5.1.7. Other Guidance

In patients experiencing neurological deterioration due to an increase of either the tumor mass or the peritumoral edema, the decision to maintain or not ipilimumab will be done case by case on the basis of clinical judgement and discussion with the Sponsor.

5.1.8. Treatment of Infusion Reactions Associated with Ipilimumab

Since ipilimumab contains only human protein sequences, it is less likely that any allergic reaction will be seen in patients. However, it is possible that infusion of ipilimumab will induce a cytokine release syndrome that could be evidenced by fever, chills, rigors, rash, pruritus, hypotension, hypertension, bronchospasm, or other symptoms. No prophylactic pre-medication will be given unless indicated by previous experience in an individual patient. Reactions should be treated based upon the following recommendations.

- For mild symptoms (e.g., localized cutaneous reactions such as mild pruritus, flushing, rash):
 - Decrease the rate of infusion until recovery from symptoms, remain at bedside and monitor patient.
 - Complete the ipilimumab infusion at the initial planned rate.
 - Diphenhydramine 50 mg IV, Dexchlorpheniramine maleate 5 mg IV, or an equivalent antihistaminic agent may be administered at the discretion of the treating physician; patients may receive additional doses with close monitoring.
 - Premedication with diphenhydramine or dexchlorpheniramine maleate may be given at the discretion of the investigator for subsequent doses of ipilimumab.
- For moderate symptoms (any symptom not listed above [mild symptoms] or below [severe symptoms] such as generalized pruritus, flushing, rash, dyspnea, hypotension with systolic BP >80 mmHg):
 - Interrupt ipilimumab.
 - Administer diphenhydramine 50 mg IV, dexchlorpheniramine maleate 5 mg IV, or an equivalent antihistaminic agent

- Monitor patient closely until resolution of symptoms.
- Corticosteroids may abrogate any beneficial immunologic effect, but may be administered at the discretion of the treating physician.
- Resume ipilimumab infusion after recovery of symptoms.
- At the discretion of the treating physician, ipilimumab infusion may be resumed at *one half the initial infusion rate, then increased incrementally to the initial infusion rate.*
- If symptoms develop after resumption of the infusion, the infusion should be discontinued and no additional ipilimumab should be administered that day.
- The next dose of ipilimumab will be administered at its next scheduled time and may be given with pre-medication (diphenhydramine and acetaminophen) and careful monitoring, following the same treatment guidelines outlined above.
- At the discretion of the treating physician additional oral or IV antihistamine may be administered prior to dosing with ipilimumab.
- For severe symptoms (e.g., any reaction such as bronchospasm, generalized urticaria, systolic blood pressure \leq 80 mm Hg, or angioedema):
 - Immediately discontinue infusion of ipilimumab, and disconnect infusion tubing from the subject.
 - Consider bronchodilators, epinephrine 1 mg IV or subcutaneously, and/or diphenhydramine 50 mg IV (or dexchlorpheniramine maleate 5 mg, or an equivalent antihistaminic agent), with methylprednisolone 100 mg IV, as needed.
 - Patients should be monitored until the investigator is comfortable that the symptoms will not recur.
 - No further ipilimumab will be administered.
- In case of late-occurring hypersensitivity symptoms (e.g., appearance within one week after treatment of a localized or generalized pruritus), symptomatic treatment may be given (e.g., oral antihistamine, or corticosteroids).

5.1.9. Treatment of Ipilimumab-Related Isolated Drug Fever

In the event of isolated drug fever, the investigator must use clinical judgment to determine if the fever is related to the ipilimumab or to an infectious etiology. If a patient experiences isolated drug fever, for the next dose, pre-treatment with acetaminophen or non-steroidal anti-inflammatory agent (investigator discretion) should be instituted and a repeated antipyretic dose at 6 and 12 hours after ipilimumab infusion, should be administered. The infusion rate will remain unchanged for future doses. If a patient experiences recurrent isolated drug fever following premedication and post dosing with an appropriate antipyretic, the infusion rate for subsequent dosing should be decreased to 50% of the previous rate. If fever recurs following infusion rate change, the investigator should assess the patient's level of discomfort with the event and use clinical judgment to determine if the patient should receive further ipilimumab.

5.1.10. Monitoring and Management of Immune-mediated Adverse Reactions

Immune-mediated Enterocolitis

Monitor patients for signs and symptoms of enterocolitis (such as diarrhea, abdominal pain, mucus or blood in stool, with or without fever) and of bowel perforation (such as peritoneal signs and ileus). In

symptomatic patients, rule out infectious etiologies and consider endoscopic evaluation for persistent or severe symptoms.

Permanently discontinue ipilimumab in patients with severe enterocolitis and initiate systemic corticosteroids at a dose of 1 to 2 mg/kg/day of prednisone or equivalent. Upon improvement to Grade 1 or less, initiate corticosteroid taper and continue to taper over at least one month. In clinical trials, rapid corticosteroid tapering resulted in recurrence or worsening symptoms of enterocolitis in some patients.

Withhold ipilimumab dosing for moderate enterocolitis; administer anti-diarrheal treatment and, if persistent for more than one week, initiate systemic corticosteroids at a dose of 0.5 mg/kg/day prednisone or equivalent.

Immune-mediated Hepatitis

Monitor liver function tests (hepatic transaminase and bilirubin levels) and assess patients for signs and symptoms of hepatotoxicity before each dose of ipilimumab. In patients with hepatotoxicity, rule out infectious or malignant causes and increase frequency of liver function test monitoring until resolution.

Permanently discontinue ipilimumab in patients with Grade 3–5 hepatotoxicity and administer systemic corticosteroids at a dose of 1 to 2 mg/kg/day of prednisone or equivalent. When liver function tests show sustained improvement or return to baseline, initiate corticosteroid tapering and continue to taper over 1 month. Across the clinical development program for ipilimumab, mycophenolate treatment has been administered in patients who have persistent severe hepatitis despite high-dose corticosteroids. Withhold ipilimumab in patients with Grade 2 hepatotoxicity.

Immune-mediated Dermatitis

Monitor patients for signs and symptoms of dermatitis such as rash and pruritus. Unless an alternate etiology has been identified, signs or symptoms of dermatitis should be considered immune-mediated.

Permanently discontinue ipilimumab in patients with Stevens-Johnson syndrome, toxic epidermal necrolysis, or rash complicated by full thickness dermal ulceration, or necrotic, bullous, or hemorrhagic manifestations. Administer systemic corticosteroids at a dose of 1 to 2 mg/kg/day of prednisone or equivalent. When dermatitis is controlled, corticosteroid tapering should occur over a period of at least 1 month. Withhold ipilimumab dosing in patients with moderate to severe signs and symptoms.

For mild to moderate dermatitis, such as localized rash and pruritus, treat symptomatically. Administer topical or systemic corticosteroids if there is no improvement of symptoms within 1 week.

Immune-mediated Neuropathies

Monitor for symptoms of motor or sensory neuropathy such as unilateral or bilateral weakness, sensory alterations, or paresthesia. Permanently discontinue ipilimumab in patients with severe neuropathy (interfering with daily activities) such as Guillain-Barré-like syndromes. Institute medical intervention as appropriate for management of severe neuropathy. Consider initiation of systemic corticosteroids at a dose of 1 to 2 mg/kg/day prednisone or equivalent for severe neuropathies. Withhold ipilimumab dosing in patients with moderate neuropathy (not interfering with daily activities).

Immune-mediated Endocrinopathies

Monitor patients for clinical signs and symptoms of hypophysitis, adrenal insufficiency (including adrenal crisis), and hyper- or hypothyroidism. Patients may present with fatigue, headache, mental status changes, abdominal pain, unusual bowel habits, and hypotension, or nonspecific symptoms which may resemble

other causes such as brain metastasis or underlying disease. Unless an alternate etiology has been identified, signs or symptoms of endocrinopathies should be considered immune-mediated.

Monitor thyroid function tests and clinical chemistries at the start of treatment, before each dose, and as clinically indicated based on symptoms. In a limited number of patients, hypophysitis was diagnosed by imaging studies through enlargement of the pituitary gland. Withhold ipilimumab dosing in symptomatic patients. Initiate systemic corticosteroids at a dose of 1 to 2 mg/kg/day of prednisone or equivalent, and initiate appropriate hormone replacement therapy.

Other Immune-mediated Adverse Reactions, Including Ocular Manifestations

The following clinically significant immune-mediated adverse reactions were seen in less than 1% of ipilimumab-treated patients in Study 1: nephritis, pneumonitis, meningitis, pericarditis, uveitis, iritis, and hemolytic anemia.

Across the clinical development program for ipilimumab, the following likely immune-mediated adverse reactions were also reported with less than 1% incidence: myocarditis, angiopathy, temporal arteritis, vasculitis, polymyalgia rheumatica, conjunctivitis, blepharitis, episcleritis, scleritis, leukocytoclastic vasculitis, erythema multiforme, psoriasis, pancreatitis, arthritis, and autoimmune thyroiditis.

Permanently discontinue ipilimumab for clinically significant or severe immune-mediated adverse reactions. Initiate systemic corticosteroids at a dose of 1 to 2 mg/kg/day prednisone or equivalent for severe immune-mediated adverse reactions.

Administer corticosteroid eye drops to patients who develop uveitis, iritis, or episcleritis. Permanently discontinue ipilimumab for immune-mediated ocular disease that is unresponsive to local immunosuppressive therapy.

5.1.11. Liver Function Test (LFT) Assessments Required Before Administration of Ipilimumab

Liver function tests (AST, ALT, T. bilirubin) will be evaluated for every subject prior to administration of ipilimumab. Blood samples must be collected and analyzed at local or central labs within 3 days prior to dosing. LFT results must be reviewed by the principal investigator (or designee) to meet dosing criteria specifications: $\leq 2.5 \times \text{ULN}$ for AST, ALT and $\leq 1.5 \times \text{ULN}$ for T. bilirubin unless liver metastases are present in which case LFT $\leq 5 \times \text{ULN}$ for AST, ALT and T. bilirubin $\leq 3.0 \times \text{ULN}$ prior to dosing.

If, during the course of treatment abnormal LFT values are detected, the subject must be managed using the hepatotoxicity algorithm section of the ipilimumab Investigators.

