Study Schema: Drugs / Doses / Length of Treatment)	
 • Ipilimumab 3mg/Kg iv q 3 weeks for 4 cycles • WBRT 30 Gy in 10 fractions (or radiobiological equivalent schedule, after Sponsor approval), starting between C1D2 and C2D1
Study Objectives: Primary: Secondary:	
Primary Objective
 
 • Efficacy - Primary endpoint: 1-year survival rate 
Secondary Objectives
 
 • Efficacy – Endpoints: 
 ○ Progression-Free survival-PFS (median, 6-month PFS rate) 
 ▪ Intracranial PFS (median, 6-month PFS rate)

	
 ▪ Extracranial PFS (median, 6-month PFS rate) 
 ○ Overall survival (median) ○ Response rate: (global, intracranial, extracranial) (“Immune-related response criteria”) ● Safety: Adverse Event rates ● Feasibility: dose delays/reductions, treatment exposure
Study Design:	Multicenter, single arm, phase 2 clinical study on the combination of radiation therapy and ipilimumab
Accrual Goal: (Total number of patients)	56 patients treated 66 included
Accrual Rate: (Number of patients expected per month)	3 to 4 patients per month
FPFV: LPFV: Follow Up: (dd-mm-yy)	03/2014 10/2015 10/2016
Correlative Studies: (PK/PD, etc.)	
Exploratory Objectives.
 
 ○ Potential baseline predictors of efficacy (in tumor tissue and peripheral blood) 
Potential early surrogates for response: inpatient variation of quantitative apparent diffusion coefficients of serial diffusion-weighted magnetic resonance imaging

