4.1 Inclusion Criteria

- 1) Willing and able to give written informed consent.
- 2) Histologic diagnosis of melanoma.
- 3) First episode of radiological evidence of brain metastases
- 4) Age > 18 years.
- 5) RTOG-RPA class 2 (Table 1)
- 6) Karnofsky performance status (PS) > 70%. (Appendix 1)
- 7) Barthel Index of Activities of Daily Living > 10 (Appendix 2)
- 8) Measurable disease (mWHO criteria).
- 9) Adequate organ function as determined by the following criteria:
 - a. WBC \geq 2000/uL
 - b. Absolute neutrophil count (ANC) $> 1.5 \times 10^9/L$.
 - c. Platelet count $> 75 \times 10^9/L$.
 - d. Hemoglobin > 9 g/dL. If the patient received a RBC transfusion, the required value of hemoglobin should be met at least 1 week after the most recent transfusion.
 - e. Serum creatinine $\leq 2.0 \times$ ULN.
 - f. Serum aspartate aminotransferase (AST) and serum alanine aminotransferase (ALT) $\leq 2.5 \times$ ULN for patients without liver metastasis, or ≤ 5 times for liver metastases.
 - g. Total bilirubin $\leq 2.0 \times$ ULN, (except patients with Gilbert's Syndrome, who must have a total bilirubin less than 3.0 mg/dL)
 - h. Albumin > 2.5 g/dL
- 10) Persons of reproductive potential must agree to use an adequate method of contraception throughout treatment and for at least 26 weeks after ipilimumab is stopped:
 - a. WOCBP include any female who has experienced menarche and who has not undergone successful surgical sterilization (hysterectomy, bilateral tubal ligation, or bilateral oophorectomy) or is not post-menopausal. WOCBP must have a negative serum or urine pregnancy test (minimum sensitivity 25 IU/L or equivalent units of HCG) within 72 hours before the start of ipilimumab. If the pregnancy test is positive, the patient must not receive ipilimumab and must not be enrolled in the study. Before study enrollment, women of childbearing potential (WOCBP) must be advised of the importance of avoiding pregnancy during study participation and the potential risk factors for an unintentional pregnancy. WOCBP must be using an adequate method of contraception to avoid pregnancy throughout the study and for up to 26 weeks after the last dose of investigational product, in such a manner that the risk of pregnancy is minimized. In general, the decision for appropriate

methods to prevent pregnancy should be determined by discussions between the investigator and the study subject.

- Post-menopause is defined as:

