5.1.5. Permanent Discontinuation of Ipilimumab

5.1.5.a Permanent Discontinuation for Related Adverse Events

Permanently discontinue ipilimumab for any of the following:

- Persistent moderate adverse reactions or inability to reduce corticosteroid dose to 7.5 mg prednisone or equivalent per day (due to an AE).
- Failure to complete full treatment course within 18 weeks from administration of first dose.
- Severe or life-threatening adverse reactions, including any of the following:
 - Colitis with abdominal pain, fever, ileus, or peritoneal signs; increase in stool frequency (7 or more over baseline), stool incontinence, need for intravenous hydration for more than 24 hours, gastrointestinal hemorrhage, and gastrointestinal perforation
 - Aspartate aminotransferase (AST) or alanine aminotransferase (ALT) >5 times the upper limit of normal or total bilirubin >3 times the upper limit of normal
 - Stevens-Johnson syndrome, toxic epidermal necrolysis, or rash complicated by full thickness dermal ulceration, or necrotic, bullous, or hemorrhagic manifestations
 - Severe motor or sensory neuropathy, Guillain-Barré syndrome, or myasthenia gravis
 - Severe immune-mediated reactions involving any organ system (eg, nephritis, pneumonitis, pancreatitis, non-infectious myocarditis)
 - Immune-mediated ocular disease that is unresponsive to topical immunosuppressive therapy

- Any adverse event, laboratory abnormality or intercurrent illness which, in the judgment of the investigator, presents a substantial clinical risk to the patient with continued dosing.
- The development of progression (irPD) in the global tumor burden confirmed by serial imaging 4-6 weeks later and/or clinical deterioration of subject's condition such that further benefit from ipilimumab dosing is unlikely or requires a change of therapy.

Please refer to the IB for specific treatment algorithms.

The following neurological adverse event requires permanent discontinuation of ipilimumab and defines unacceptable neurotoxicity:

- Any motor neurologic toxicity \geq Grade 3 regardless of causality
- Any \geq Grade 3 treatment related sensory neurologic toxicity

Please refer to the IB for specific treatment algorithms.

5.1.5.b Exceptions to Permanent Discontinuation

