6. STUDY PROCEDURES AND OBSERVATIONS

6.1. Time and Events Schedule (Table 12)

Visit	Visit 1 Registration (Day -28 to day -1)	Visit 2 Eligibility (Day -7 to day -1)	Visit 3. C1D 1	Visits R.1 to R.x Starting Between C1D2 and C2D1	Visit 4 C2D 1	Visit 5 C3D 1	Visit 6 C4D 1	End of treatment C4D30(±2)	Follow-up Tumor Assesment (every 9 weeks +/- 1)	Follow up visits Months 6, 9, 12, 15, 18, 21, 24, 27, 30 (+/- 1 week)
Informed Consent Form	X									
Central registration	X									
Medical History		X(1)								
Concomitant diseases		X(1)	X	X	X	X	X	X		X
Symptoms		X	X	X	X	X	X	X		X
Karnofsky PS,Barthel Index, Physical exam, vital constants, body weight		X	X	X	X	X	X	X		X
Neurological exam		X	X	X	X	X	X	X		X
Concomitant medications		X	X	X	X	X	X	X		X
RPA class		X								
Inclusion/Exclusion checklist		X								
Eligibility communication		X								
Blood Workup										
Hematology		X		X	X	X	X	X		X
Biochemistry		X		X	X	X	X	X		X
Pregnancy test		X(2)			X	X	X	X		
Auto-immunity panel		X(1)								
Hormones (morning cortisol and ACTH, free T4, T3, TSH, prolactin)		X(1)			X	X	X	X		X
Efficacy evaluation										

GRAY-B Study (GEM 1202). V1.0 (28 Nov 2013)

Chest-Abdomen-pelvis CT scan		X(1)						X(5)	X	X
Craneal CT scan/MRI		X(1)						X(5)	X	X
Safety evaluation										
Adverse events /SAEs	Throughout the study									
Dose reductions					Throughout the study, when applicable					
Dose delays					Throughout the study, when applicable					
Biomarker evaluation (optional)										
Archived tumour tissue		X(1)								
Peripheral blood (serum + whole blood)			X		X	X	X	X		
DW-MRI (optional)		X(3)				X(4)		X		
Intervention										
Ipilimumab infusion			C1		C2	C3	C4			
Initiation of radiation therapy				X						

(1) Can be performed between d-28 and d-1.

(2) All WOCBP MUST have a negative pregnancy test within 72 hours before receiving ipilimumab. The minimum sensitivity of the pregnancy test must be 25 IU/L or equivalent units of HCG. If the pregnancy test is positive, the subject must not receive ipilimumab and must not be enrolled in the study.

(3) If done, it should be performed up to 2 weeks prior to C1D1

(4) If applicable, 4 weeks (± 1) after the end of WBRT

(5) Should be done on week 12+1

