Laboratory tests are obtained as part of screening and to determine eligibility. Results of safety laboratory collections (ie, Chemistry and Hematology) must be obtained and reviewed in advance of study drug dosing.

- The following lab parameters must be collected within a window of up to 1 day prior to dosing: CBC/diff (includes ANC and ALC), AST, ALT, total bilirubin, CRP, sodium, chloride, bicarbonate, BUN

or urea, creatinine, and glucose. Baseline values up to 7 days before the first dose are acceptable prior to C1. These lab tests will also be performed at week 12, EOT, and 90 days after last dose administration of ipilimumab (+/-1 week).

- CBC/diff, AST, ALT, total bilirubin, sodium, chloride, BUN or urea, creatinine, and glucose will also be collected weekly during WBRT

All protocol-specified laboratory tests will be analyzed and reported by a local lab.

Importantly, **LFT results (AST, ALT, and total bilirubin) must be reviewed within 24 h prior to dosing**. If abnormal LFTs are detected, the subject must be managed using the hepatotoxicity algorithm in the SMPC. (Additional draws must be incorporated when monitoring recovery from any non-hematologic AE (eg, elevations in ALT, AST).

6.4.1.f Endocrine Tests

The following endocrine tests should be performed at Screening and prior to each dosing visit: TSH, free T4 and T3, morning ACTH and cortisol, and prolactin.

Other hormones might be tested as well as clinically indicated.

During treatment, if patient is asymptomatic, it will be adequate to confirm at least the normality of the results of the tests performed within the last 3 weeks. If the patient is symptomatic (e.g. asthenia, cephalgia) it will be mandatory to check the results of the pre-dose testing (at least 72 h prior to dose administration)

6.4.1.g HIV and Hepatitis Panel

At screening, testing for HIV, hepatitis C antibody, and hepatitis B surface antigen (HBsAg) should be performed for clinically suspected HIV, HBV, and HCV. If positive results at Screening are not indicative of true active or chronic infection, the subject may enter the study after discussion and agreement between the Investigator and the Medical Monitor. These tests will be repeated during the course of the study if clinically indicated.

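### Without liver metastases, the bilirubin entry limit (inclusion 9g) is looser than the dosing limit (5.1.11), so an eligible patient can be refused the first ipilimumab dose

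*Protocol*

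**What the plan says.** **Entry.** Protocol Section 4.1, inclusion 9g, and the matching synopsis line cap total bilirubin at 2.0 x ULN, whether or not there are liver metastases. Patients with Gilbert's Syndrome are excepted from that cap, "who must have a total bilirubin less than 3.0 mg/dL".

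**Dosing.** Section 5.1.11 states that "Liver function tests (AST, ALT, T. bilirubin) will be evaluated for every subject prior to administration of ipilimumab", and that "LFT results must be reviewed by the principal investigator (or designee) to meet dosing criteria specifications". The limit it then sets is 1.5 x ULN "for T. bilirubin unless liver metastases are present in which case LFT" limits rise to 5 x ULN for AST and ALT and 3.0 x ULN for bilirubin. The section mentions neither Gilbert's Syndrome nor a separate rule for cycle 1.

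**Timing.** Table 12 (Section 6.1) puts biochemistry at the eligibility visit (day -7 to day -1) and lists none at C1D1. Section 6.4.1.e adds: "Baseline values up to 7 days before the first dose are acceptable prior to C1".

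**Waivers.** Section 4 rules out exceptions to the selection criteria, and Section 3 says the sponsor will allow no protocol exceptions.

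**The concern.** An entry criterion should not admit a patient whom the protocol forbids the site to treat on the same laboratory value. For bilirubin without liver metastases the protocol does this. The patient consents, meets 9g, is included, and is then held at C1D1.

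For Gilbert patients the matter is sharper. The protocol goes out of its way to admit them, but without liver metastases the exception has no effect at dosing once bilirubin exceeds 1.5 x ULN. If the value stays there, retesting will not help.

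What is at stake is operational: a delayed or missed first dose, uncertainty at sites about which bilirubin rule governs dose 1, and an included patient who contributes to neither the Treated nor the Evaluable set, since both require at least one ipilimumab dose (Section 9.2).

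**Working it through.** No sample-size or power figure is involved. The check sets the two sets of limits side by side.

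| Patient group | Entry (9g) | Dosing (5.1.11) | Meets entry but cannot be dosed |
|---|---|---|---|
| No liver metastases, no Gilbert | up to 2.0 x ULN | up to 1.5 x ULN | above 1.5, up to 2.0 x ULN |
| No liver metastases, Gilbert | below 3.0 mg/dL | up to 1.5 x ULN | above 1.5 x ULN, below 3.0 mg/dL |
| Liver metastases, no Gilbert | up to 2.0 x ULN | up to 3.0 x ULN | none |

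For AST and ALT the limits agree at entry and dosing: 2.5 x ULN, or 5 x ULN with liver metastases. The mismatch is therefore in bilirubin only, and for non-Gilbert patients only where there are no liver metastases.

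**Non-Gilbert band.** Both limits are multiples of ULN, so the band exists whatever the local ULN is.

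**Gilbert band.** Here one limit is in mg/dL and the other is a multiple of ULN. The band exists when 1.5 x ULN < 3.0 mg/dL, that is, when ULN < 3.0 / 1.5 = 2.0 mg/dL. The documents give no ULN, so the figures below are assumptions:

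| Assumed ULN (mg/dL) | Dosing limit, 1.5 x ULN | General entry limit, 2.0 x ULN | Non-Gilbert band (mg/dL) | Gilbert band (mg/dL) |
|---|---|---|---|---|
| 1.0 | 1.5 | 2.0 | above 1.5 to 2.0 | above 1.5 to below 3.0 |
| 1.2 | 1.8 | 2.4 | above 1.8 to 2.4 | above 1.8 to below 3.0 |

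**Can one sample pass one rule and fail the other?** Yes. A biochemistry sample taken the day before C1D1 falls within the eligibility-visit window and within the pre-dose sampling windows. With an assumed ULN of 1.0 mg/dL, a value of 1.8 mg/dL is 1.8 x ULN: it passes 9g (2.0 or less) and fails 5.1.11 (above 1.5).

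**Does another section resolve it?** None does.

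- Section 6.4.1.e relaxes how old the baseline sample may be, not the limit it must meet.
- Section 6.2.1 requires laboratory results to be in range before ipilimumab, which points back to the dosing limit.
- Section 5.1.3 covers skipping doses for adverse events and Section 5.1.5 covers permanent discontinuation. Neither clears a patient for dose 1.

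**The case against.** The strongest reply is that a dosing limit may properly be stricter than an entry limit, and that nothing harmful follows. The rule withholds drug. Section 5.1.11 is a pre-dose check that neither removes the patient nor forbids a retest and a later C1D1. Exclusion 13 also lets the investigator decline a patient for whom ipilimumab would be hazardous. The documents give no bilirubin distribution, no Gilbert frequency and no ULN, so there is no evidence that any patient falls in the band. Nor do they say which limit was intended, so the direction of the correction is open.

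Most of this stands, and it is why the point is minor. What does not stand is the idea of a deliberate two-tier rule. AST and ALT carry the same limits at both stages, and a single pre-dose sample can serve both bilirubin rules. A Gilbert exception given at entry and absent at dosing also looks like an omission.

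Three stronger readings might be inferred, and the documents do not support them:

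- *Patients will be dosed unsafely.* Followed as written, 5.1.11 does the opposite.
- *The affected patient is barred for good.* A lower repeat value permits dosing.
- *Accrual or the primary analysis is at risk.* The accrual goal, "56 patients treated 66 included", already allows for included patients who are not treated, and nothing indicates how many would be lost this way.

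**Conclusion.** The inconsistency is real and the text is wrong as written, but it is minor. Without liver metastases, a patient above 1.5 and up to 2.0 x ULN can meet entry and be refused dose 1 unless a repeat value is lower. So can a Gilbert patient above 1.5 x ULN and below 3.0 mg/dL. The first statement needs no assumption about ULN; the second needs a local ULN below 2.0 mg/dL. The effect is fail-safe. The number affected cannot be derived from the documents and is probably small. The 56-patient sample size, the rule of at least 17 one-year survivors out of 56, and the error rates are unchanged.

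**What to change.** Make inclusion 9g, the synopsis line and Section 5.1.11 agree.

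- **Default.** Set entry at total bilirubin 1.5 x ULN or less for patients without liver metastases, and keep 2.0 x ULN for those with them. This loosens no dosing limit and turns away almost nobody who could have been dosed. Raising 5.1.11 to 2.0 x ULN would also remove the conflict, but it relaxes a dosing limit. The sponsor should confirm which limit is intended.
- **Gilbert's Syndrome.** The sponsor should either carry the below-3.0 mg/dL exemption into 5.1.11 or remove it from 9g.

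The cost is a wording change in 9g and the synopsis, plus one Gilbert sentence added to 5.1.11 or deleted from 9g and the synopsis. The downside of the default is that a few patients above 1.5 and up to 2.0 x ULN are retested before enrolment or not enrolled. No change to the sample size or the analysis is needed.
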